6 TREATMENT PROCEDURES

6.1 Composition, Formulation, and Storage

At study sites, all study medication will be stored as described in the appropriate prescribing information for that country (if applicable) or the pharmacy manual and inventoried in accordance with applicable state and federal regulations.

6.1.1 Investigational Treatment: Cabozantinib

Cabozantinib tablets are supplied as film coated tablets containing cabozantinib malate equivalent to 20 mg and 60 mg of cabozantinib and contain microcrystalline cellulose, lactose anhydrous, hydroxypropyl cellulose, croscarmellose sodium, colloidal silicon dioxide, magnesium stearate and Opadry® yellow. The 60-mg tablets are oval and the 20-mg tablets are round. Doses of 40 mg will comprise two 20-mg tablets. The components of the tablets are listed in Table 6-1.

Table 6-1: Cabozantinib Tablet Components and Composition

Ingredient	Function	% w/w ^a
Cabozantinib Drug Substance (25% drug load as free base)	Active Ingredient	31.68
Microcrystalline Cellulose (Avicel® PH-102)	Filler	38.85
Lactose Anhydrous (60M)	Filler	19.42
Hydroxypropyl Cellulose (EXF)	Binder	3.00
Croscarmellose Sodium (Ac-Di-Sol®)	Disintegrant	6.00
Colloidal Silicon Dioxide	Glidant	0.30
Magnesium Stearate	Lubricant	0.75
Opadry® yellow film coating which includes HPMC 2910/hypromellose 6 cp, titanium dioxide, triacetin, and iron oxide yellow	Film Coating	4.00

^a weight fraction, expressed in percentage; HPMC, hydroxypropyl methylcellulose

Refer to the Pharmacy Manual for details on storage and handling of cabozantinib.

6.2 Cabozantinib Administration

Subjects will receive cabozantinib orally at a (starting) dose of 60 mg once daily.

Cabozantinib must be taken on an empty stomach. Subjects must be instructed not to eat for at least 2 hours before and at least 1 hour after taking cabozantinib. Subjects should be instructed to take their cabozantinib dose at approximately the same time every day for total of 12 weeks. If a subject misses a dose, the dose may be taken later only if it is within 12 hours of when the missed dose should have been taken. The missed dose should not be made up if it is within 12 hours of the next scheduled dose.

Cabozantinib tablets should be swallowed whole with at least 8 ounces of water. The tablets should not be crushed. Grapefruit, grapefruit juice, Seville oranges and their products should be avoided by subjects taking cabozantinib.

In all subjects, dose reductions and delays to manage toxicity are allowed under the guidelines in Section 6.3 below.

6.3 Cabozantinib Dose Modifications, Interruptions, and Discontinuation

The following should be taken into consideration in decisions regarding dose modifications (reductions or interruption):

- As a general approach all AEs should be managed with supportive care at the earliest signs of toxicity considered related to the study treatment. Should this be ineffective, dose interruptions and/or reductions should be considered to prevent worsening of toxicity.
- The assigned starting dose for cabozantinib is 60 mg/day. 2 dose reduction levels of cabozantinib are permitted (see Table 6-2).
- Dose modification criteria for cabozantinib are shown in Table 6-3. Dose interruptions and/or reductions should be implemented for unacceptable toxicity. Doses may be modified at any time while a subject is on treatment.
- Dose reductions or interruptions may also occur in the setting of lower grade toxicity than defined in Table 6-3, if the investigator feels it is in the interest of a subject’s safety and will optimize drug tolerability.
- Interruption of cabozantinib treatment for cabozantinib-related AEs may occur at any time per investigator discretion. If treatment is interrupted due to related AEs for more than 6 weeks, cabozantinib should be discontinued unless there is unequivocal evidence that the subject is benefitting. In this situation, a subject may be able to restart therapy with a dose reduction upon resolution of the toxicity per the discretion of the investigator.
- Dose interruptions for reason(s) other than related AEs (eg, surgical procedures) can be longer than 6 weeks per the discretion of the investigator.

Guidelines for the management of specific AEs are provided in Section 6.3.3.

Table 6-2: Dose Reductions of Cabozantinib

Assigned Dose	First Dose Level Reduction	Second Dose Level Reduction
60-mg cabozantinib oral qd	40-mg cabozantinib oral qd	20-mg cabozantinib oral qd
40-mg cabozantinib oral qd	20-mg cabozantinib oral qd	No dose reduction permitted
20-mg cabozantinib oral qd	No dose reduction permitted	—

qd, once daily

Cabozantinib will be discontinued if a qd dose of 20-mg cabozantinib (minimum dose) is not tolerated

Table 6-3: Dose Modifications of Cabozantinib for Treatment-Related AEs

CTCAE v.4.0 Grade	Recommended Guidelines for Management ^a
Grade 1 AEs	Add supportive care as indicated. Continue cabozantinib treatment at the current dose level if AE is manageable and tolerable.
Grade 2 AEs which are tolerable and are easily managed	Continue cabozantinib treatment at the current dose level with supportive care.
Grade 2 AEs which are intolerable and cannot be adequately managed	At the discretion of the investigator, cabozantinib should be dose reduced or interrupted. Note: It is recommended that dose holds be as brief as possible.
Grade 3 AEs (except clinically non-relevant laboratory abnormalities)	Cabozantinib should be interrupted unless the toxicity can be easily managed with a dose reduction and optimal medical care. Note: It is recommended that dose holds be as brief as possible.
Grade 4 AEs (except clinically non-relevant laboratory abnormalities)	Subjects should have cabozantinib interrupted immediately. Discontinue cabozantinib unless the following criteria are met: 
 • Subject is deriving clear clinical benefit as determined by the investigator • Toxicity can be managed with a dose reduction following recovery to Grade 1 (or baseline) and optimal medical care

AE, adverse event.

Note: The dose delay and modification criteria for specific medical conditions are provided in Section 6.3.2. For re-treatment criteria of study treatment after a dose hold see Section 6.3.1.

^a Study treatment dose adjustment is only needed if the toxicity was deemed related to cabozantinib treatment or had an unclear relationship to cabozantinib treatment.

6.3.1 Cabozantinib Dose Reinstitution and Reescalation

If the subject recovers from his or her toxicities to CTCAE v.4.0 Grade \leq 1 or to the baseline value (or lower) and the toxicity was unrelated to study treatment, then study treatment may be restarted with no change in dose.

If the subject recovers from his or her toxicities to Grade \leq 1 or to the baseline value (or lower) the toxicity was deemed possibly related to study treatment, then study treatment may be restarted at a reduced dose (see Table 6-2 for the schedule of dose reductions).

Subjects receiving a daily dose of 20 mg may be restarted at the same dose if deemed safe at the discretion of the investigator. Subjects unable to tolerate a daily dose of 20 mg should discontinue study treatment.

Re-escalation to the previous dose, (but not higher than 60 mg/day) may be allowed at the discretion of the investigator for AEs which have resolved or recovered to Grade 1 (or baseline value) and deemed tolerable and easily managed by optimized supportive treatment. Dose re-escalation is not allowed for a drug-related dose reduction triggered by Grade 4 hematologic toxicities or by Grade 4 AEs affecting major organs (eg, central nervous system, cardiac, hepatic, renal).

6.3.2 Guidelines for Management of Potential Adverse Events

Subjects will be monitored for AEs from the time of signing informed consent through their last follow-up visit (30 days after the date of the last dose of cabozantinib treatment.) Subjects will be instructed to notify their physician or other study team member immediately at the onset of any AE. Seriousness, severity grade, and relationship to study treatment of AEs will be determined by the investigator. AE severity will be graded by the investigator in accordance with CTCAE v.4.0.

Management of severe or intolerable adverse reactions may require temporary dose reduction and/or interruption for cabozantinib.

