2 STUDY OBJECTIVES AND ENDPOINTS

The objectives of this study are as follows:

Primary objective:

- To assess the objective response rate (complete and partial responses), following the administration of cabozantinib for 12 weeks in patients with locally advanced biopsy-proven non-metastatic ccRCC prior to undergoing surgery.

Secondary Objectives:

- To assess the safety, and tolerability of neoadjuvant cabozantinib.
- To determine the clinical outcome (DFS, OS) of patients with non-metastatic ccRCC who treated with neoadjuvant cabozantinib.
- To evaluate the surgery related outcomes.
- To evaluate correlative studies, including biomarkers, quality of life, and frailty/sarcopenia assessment of patients with non-metastatic ccRCC who are treated with neoadjuvant cabozantinib.

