^gPatients will undergo kidney surgery min 28 days after the last dose of cabozantinib.

^hAppendix C

ⁱAppendix D

^jIf clinically indicated

^kBlood collection post-surgical resection for correlative studies

^lOnly from female patients with child bearing potential within 72 hours of study drug

^mThese assessments may be done within 14 days of Week 1 Day 1, prior to releasing the cabozantinib.

ⁿThis scan can be done within 28 after last dose of cabozantinib

If the subject is unable to have a study assessment taken within the defined time window due to an event outside of his or her control (eg, clinic closure, personal emergency, inclement weather, vacation), the assessment should be performed as close as possible to the required schedule.

Regular tumor assessments should be performed in accordance to the guidelines in Section 5.5 to determine if PD is present.

The Treatment Period ends when a subject receives his or her last dose of study treatment; the subject then enters the Post-Treatment Period.

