5.3 Post-Treatment Period

Subjects will return to the study site within 14 days after their last dose of cabozantinib to complete end-of-study assessments. Laboratory, imaging and physical examinations will be performed. Remaining study treatment will be returned by the subject, and treatment compliance will be documented. Additional follow-up will occur for subjects with AEs related to study treatment that are ongoing at the time of this visit, and for subjects with SAEs related to study treatment that occur after the time of this visit.

This period includes intraoperative and post-operative assessments. Patients will wait a minimum of 28 days (washout period) from the last dose of cabozantinib prior to surgical resection. Patients will be assessed for intraoperative and post-operative complications using the universally recognized Clavien Dindo perioperative classification of adverse events (13). Specifically, we will examine endpoints including, but not limited, chylous ascites, pulmonary embolism, ileus, bleeding, superficial wound dehiscence, fascial dehiscence, pleural effusion, pneumonia, urinary retention, gastroparesis, anemia, and post-operative delirium. We will also collect data regarding procedure type, i.e. radical nephrectomy, partial nephrectomy, and rate of conversion from radical to partial nephrectomy.

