6.3.3.7 Skin and Subcutaneous Tissue Disorders

Wound healing and surgery: Cabozantinib has the potential to cause wound healing complications and wound dehiscence which may even occur long after a wound has been considered healed. Therefore, surgical and traumatic wounds must not only be completely healed prior to starting cabozantinib treatment but must also be monitored for wound dehiscence, wound infection and other signs of impaired wound healing while the subject is being treated with cabozantinib. If dehiscence occurs, cabozantinib treatment should not be restarted until complete healing has taken place.

Treatment with cabozantinib should be stopped at least 28 days prior to scheduled surgery. The decision to resume treatment with cabozantinib after surgery should be based on clinical judgment of adequate wound healing.

Palmar-plantar erythrodysesthesia syndrome (PPES; also known as hand-foot syndrome), skin rash (including blister, erythematous rash, macular rash, skin exfoliation, dermatitis acneiform, and papular rash), pruritus, dry skin, erythema, pigmentary changes, and alopecia have been reported with cabozantinib. All subjects on study should be advised on prophylactic measures including the use of emollients, removal of calluses, avoidance of exposure of hands and feet to hot water leading to vasodilatation, protection of pressure-sensitive areas of hands and feet, and use of cotton gloves and socks to prevent injury and keep the palms and soles dry.

Early manifestations include tingling, numbness, mild hyperkeratosis, and symmetrical red and swollen areas on the palms and soles. The lateral sides of the fingers or periungual zones may also be affected. Adequate interventions are required to prevent worsening of skin symptoms such as blisters, desquamations, ulcerations, or necrosis of affected areas. Analgesics may be required for pain control.

Aggressive management of symptoms is recommended, including early dermatology referral. Treatment recommendations in response to PPES are summarized in Table 6-6.

Table 6-6: Management of Hand-Foot Syndrome (PPES) Associated with Cabozantinib

CTCAE v.4.0 Grade	Action To Be Taken

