8 SAFETY

8.1 Adverse Events and Laboratory Abnormalities

8.1.1 Adverse Events (AEs)

An AE is any untoward medical occurrence in a patient or clinical trial subject administered a medicinal product and which does not necessarily have a causal relationship with this treatment.

An adverse event can therefore be any unfavorable and unintended sign (e.g. an abnormal laboratory finding), symptom, or disease temporarily associated with the use of a medicinal product, whether or not considered related to the medicinal product. An adverse event can arise from any use of the drug (e.g. off-label use, use in combination with another drug) and with any route of administration, formulation, or dose, including an overdose. This definition also includes AEs associated with medication errors and uses of the investigational product outside what is in the protocol, including misuse and abuse. Pre-existing medical conditions that worsen during the study should be recorded as AEs. Abnormal laboratory values, ECG findings, or vital signs are to be recorded as AEs if they meet the criteria described in in Section 6.

All untoward events that occur after informed consent through 30 days after the decision to discontinue study treatment (or the date the subject is deemed to be a screen failure) are to be recorded by the investigational site. This requirement includes AEs from unscheduled as well as scheduled visits.

The investigator (or physician designee) is responsible for verifying and providing source documentation for all adverse events and assigning the attribution for all adverse events for subjects enrolled.

Attribution is the relationship between an adverse event or serious adverse event and the study treatment. Attribution will be assigned as follows:

- Definite – The AE *is clearly related* to the study treatment.
- Probable – The AE *is likely related* to the study treatment.
- Possible – The AE *may be related* to the study treatment.
- Unlikely – The AE *is doubtfully related* to the study treatment.
- Unrelated – The AE *is clearly NOT related* to the study treatment.

Adverse event terms recorded on the CRFs will be mapped to preferred terms using the Medical Dictionary for Regulatory Activities (MedDRA). Seriousness, severity grade, and relationship to study treatment will be assessed by the investigator. Severity grade will be defined by the current version of the National Cancer Institute (NCI)-Common Terminology Criteria for Adverse Events (CTCAE).

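### For a patient who completes treatment, all-cause adverse event recording covers at most two days after surgery, and Clavien-Dindo grading has no stated observation period

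*Combined protocol and SAP*

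**What the plan says.** **When AE collection ends.** Section 6.3.2 monitors AEs from consent "through their last follow-up visit (30 days after the date of the last dose of cabozantinib treatment". Section 8.1.1 sets the recording rule on a different anchor: "All untoward events that occur after informed consent through 30 days after the decision to discontinue study treatment". The all-cause part of Section 8.1.4 (SAEs) uses the same anchor as 8.1.1, and so does Section 8.2.4 when it fixes the status of other continuing AEs. The plan does not say what the decision date is for a patient who simply finishes 12 weeks.

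**When surgery happens.** Table 5-1, footnote g, schedules "kidney surgery min 28 days after the last dose of cabozantinib". Section 5.3 repeats the 28-day minimum. Neither gives a latest date.

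**What happens after treatment.** Under Section 5.3, "Subjects will return to the study site within 14 days after their last dose of cabozantinib to complete end-of-study assessments". After that visit, "Additional follow-up will occur for subjects with AEs related to study treatment that are ongoing at the time of this visit", and also for treatment-related SAEs that arise later. For the operation itself, "Patients will be assessed for intraoperative and post-operative complications using the universally recognized Clavien Dindo perioperative classification of adverse events". Section 5.3 then gives an open list of twelve complication types, including superficial wound and fascial dehiscence. It states no observation period.

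**What is reportable without a time limit.** The second part of Section 8.1.4 keeps SAEs related to study treatment or study procedures, even beyond 30 days. Section 8.1.2 makes a surgical complication that prolongs hospitalization an SAE.

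**Objectives and analysis.** The secondary objectives include safety and tolerability, and "To evaluate the surgery related outcomes". Section 9 summarizes AEs by frequency and percentage. It does not mention Clavien-Dindo or any other surgical outcome.

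**The concern.** In a neoadjuvant trial, part of the safety question is what happens to patients once they are operated on after the drug. The AE clock is set by dosing and runs out at about the time the operation takes place. Section 6.3.3.7 itself warns that "Cabozantinib has the potential to cause wound healing complications and wound dehiscence which may even occur long after a wound has been considered healed". All-cause recording matters most in this period: in a single-arm trial it is hard to decide whether an event some weeks after the last dose comes from the drug, the operation or neither, and recording everything avoids depending on that judgement.

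Two things are at stake. First, the AE summary would describe treatment and washout with little from the postoperative period. Second, the instrument that does cover the operation has no common end date, so a complication rate would depend on how long each patient happened to be observed.

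**Working it through.** The plan states no figure for postoperative coverage, so there is none to reproduce. The check is day arithmetic and a comparison of sections.

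**Inputs.** End of AE monitoring: day 30 after the last dose (6.3.2). End of all-cause recording: 30 days after the decision to discontinue (8.1.1, first part of 8.1.4). Earliest surgery: day 28 after the last dose (5.3; Table 5-1, footnote g). End-of-study visit: day 14 at the latest (5.3).

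**Step 1: postoperative days covered for a completer.** Let S be the day of surgery counted from the last dose, with S at least 28 and the day of surgery as postoperative day 0. Assume that the decision date is the last-dose date. Coverage = max(0, 30 − S).

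| S | Postoperative days covered |
|---|---|
| 28 | 30 − 28 = 2 |
| 29 | 30 − 29 = 1 |
| 30 | 0 (day of surgery only) |
| 31 or later | 0 (surgery itself falls outside) |

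**Step 2: sensitivity to the anchor.** If the decision comes d days after the last dose, as it may for a non-completer after a dose hold, coverage under 8.1.1 is max(0, 30 + d − S). With S = 28, d = 14 gives 30 + 14 − 28 = 16 days, and d = 42 gives 30 + 42 − 28 = 44 days. Both lags are illustrative. Section 6.3.2 would still stop at day 30 for the same patients, so the two sections diverge.

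**Step 3: does other text extend the window?**
- Section 5.3: the visit falls at least 28 − 14 = 14 days before surgery. The AE follow-up added after it is limited to treatment-related AEs already ongoing and treatment-related SAEs.
- Table 5-1: AEs appear as continuous on treatment, with one mark that seems to belong to the post-treatment column, headed as within 14 days of the last dose. The table is flattened in the available text, so this reading is cautious. No dated postoperative AE visit is visible.
- Section 5.4: contacts are every 3 months after surgery. The only AE provision is for patients removed for unacceptable AEs.
- Section 3 places the postoperative phase in the Post-Treatment Period, while 5.4 starts long-term follow-up after surgery. No day separates them.

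None of these extends all-cause collection.

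**Step 4: what remains uncollected after day 30?**
- Surgical complications: collected through Clavien-Dindo, with no cap and no seriousness or attribution filter.
- SAEs related to treatment or study procedures: collected without limit.
- Non-serious AEs not graded as surgical complications: not recorded if they arise after the window closes.
- SAEs judged unrelated to treatment and to procedures: outside both parts of 8.1.4.

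**Step 5: window needed.** To reach postoperative day 30 (an illustrative horizon), collection must run to day S + 30: day 58 if S = 28, day 72 if S = 42. The added time over day 30 is S days.

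**The case against.** The strongest defence is that the plan has two instruments by design: a drug-AE window tied to dosing, and a separate surgical-complication assessment. That is coherent for a small single-arm trial, and much of the defence stands.

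- A reader might infer that postoperative wound problems go uncollected. They do not: both kinds of dehiscence are named in Section 5.3, outside any 30-day limit. What is missing for them is a defined length of observation.
- A reader might infer that serious postoperative events escape reporting. Those related to treatment or study procedures remain reportable indefinitely. Kidney surgery is a row in Table 5-1, so it can reasonably be read as a study procedure, although the documents do not say so. If it is not one, more serious events fall outside the rule.
- A reader might infer that Section 9 drops postoperative events from the AE summary. It sets no time cut-off. Events will be absent because they were never recorded.

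The defence does not supply a Clavien-Dindo observation period, an analysis of it, or a definition of the decision date for completers. Nor does it explain why all-cause recording should stop just as the operation takes place.

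**Conclusion.** The point holds in limited form and should be fixed. For a completer, recording of AEs and SAEs regardless of cause covers 0 to 2 postoperative days. This assumes that the decision date equals the last-dose date. Under Section 8.1.1 a later decision date lengthens coverage; under Section 6.3.2 it does not.

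The content lost is non-serious postoperative AEs not graded as surgical complications, and SAEs judged unrelated to treatment or procedures. The documents give no basis for estimating how many such events there would be. Separately, Clavien-Dindo results would rest on unequal and unstated observation times and have no planned summary, although they bear on a secondary objective.

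The documents do not support a claim that postoperative safety data as a whole are lost. The week-12 response endpoint is not touched.

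**What to change.** 1. Use one anchor in Sections 6.3.2, 8.1.1, 8.1.4 and 8.2.4. Collect all AEs and SAEs regardless of attribution through a fixed period after surgery (for example 30 days), or through 30 days after the last dose if no surgery is done.
2. Apply the same window to the Clavien-Dindo assessment in Section 5.3.
3. Add a line to Section 9 that summarizes complications by Clavien-Dindo grade over that window.
4. State whether the nephrectomy counts as a study procedure for SAE reporting.

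These changes concern data collection and analysis only; the timing of surgery is left as it is.

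**Cost.** With a 30-day postoperative window, AE collection lengthens by S days per patient: at least 28, and more if surgery is later. A postoperative contact or chart review is needed at the end of the window, and there will be more reports of expected surgical events. This applies to at most 17 patients, who are already under surgical care. If the sponsor prefers to keep the drug-AE window tied to dosing, items 2 and 3 with a reconciled anchor would resolve the surgical-outcome part, but would leave the AE gap described above.
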